7.0 STATISTICAL PLAN

7.1 Sample Size Determination

Sample size was based upon the average number of cases per year that meet inclusion for the study based upon previous diagnostic and surgical logs

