Phase	N/A, This is not a clinical trial, it is one of imaging modalities
Methodology/Study Design	Prospective, non-randomized, double blind study
Study Duration	2 years
Study Center(s)	Single-center
Objectives	In this study, we aim to explore which imaging modality or combination of imaging methods, in conjunction with clinical and histological examination, will most accurately predict the presence or absence of invasion of the mandible or maxilla by intraoral squamous cell carcinoma (SCC)
Number of Subjects	20
Diagnosis and Main Inclusion Criteria	Inclusion: SCC of the oral cavity Exclusion: prior mandibular surgery, primary intraosseous carcinoma, prior history of radiation to the mandible, obvious finding of clinical invasion of the mandible, age under 18 years old
Study Therapy, Dose, Route, Regimen	N/A
Duration of administration and follow-up	N/A
Reference therapy	N/A
Statistical Methodology	Sensitivity and specificity of mandibular or maxillary invasion will be determined, in addition to true and false positive as well as true and false negative. Finally the positive and negative predictive values for each of the imaging modalities will be calculated based upon the previously mentioned statistical analysis.
Schema	See attached schema in the appendix section at the end

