5.4 Method for Assigning Subjects to Treatment Groups

This study will not be randomized. All patients will received a helical CT, PET/CT and CBCT

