6.0 STUDY PROCEDURES

6.1 Study Visit Schedule

Screening: Once patients are referred to the OMFS or JHNS departments with oral SCC, they will be evaluated to see if they meet the inclusion criteria and do not satisfy the exclusion criteria. Once they are deemed a candidate for the study by one of the involved doctors, they will have an appointment setup for a CBCT

Visit 1: CBCT in OMFS Office

Visit 2: Surgical planning in JHNS office, blinded to the result of the CBCT

Definitive Surgical Treatment

Follow-up: The patient will follow up in the JHNS department for necessary adjuvant therapies and post-surgical care when surgical treatment is carried out.

Please see the appendix for an outline of the study and also a card that will be posted in both JHNS and OMFS office to be used when evaluating patients for inclusion

Procedures, situations, or materials that may be hazardous to personnel and the relevant precautions, should also be outlined here.

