7.3 Subject Population(s) for Analysis

This section should be very specific in defining the subject populations whose data will be subjected to the study analysis – both for the primary analysis and any applicable secondary analyses.

The data from all of the subjects that are enrolled and have consented to be a part of the study will be analyzed.

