10.2.1 Independent External and Internal Audits

In addition to review by the DSMC, all studies initiated by KCC investigators are audited by an independent auditor once they have achieved 10% of target accrual. However, a study can be audited at any time based on recommendations by the IRB, DSMC, CCRRC and/or the Director of Clinical Investigations, KCC. Studies are re-audited once they have achieved 50% of target accrual. Special audits may be recommended by the IRB, DSMC or CCRRC based on prior findings, allegations of scientific misconduct and where significant irregularities are found through quality control procedures. Any irregularities identified as part of this process would result in a full audit of that study.

In addition to the audits at 10 and 50%, the CRMO randomly audits at least 10 percent of all patients entered into therapeutic KCC trials and other trials as necessary, on at least a bi-annual basis, to verify that there is a signed and dated patient consent form, the patient has met the eligibility criteria, and that SAEs are documented and reported to the TJU IRB.

All audit reports are submitted to the DSMC for review and action (when appropriate). A copy of this report and recommended DSMC action is sent to the CCRRC and TJU IRB. The committee regards the scientific review process as dynamic and constructive rather than punitive. The review process is designed to assist Principal Investigators in ensuring the safety of study subjects and the adequacy and accuracy of any data generated. The TJU IRB may, based on the DSMC and auditor's recommendation, suspend or terminate the trial.

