13.0 PUBLICATION PLAN

Once imaging and histologic data have been collected from the target sample size, the information will be compiled for publication. This information will not be published in any manner prior to official publication

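### The Study Summary gives 20 subjects, the appendix it points to labels the patient cohort N=10, and section 7.1 contains no figure that reconciles the two

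*Combined protocol and SAP*

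**What the plan says.** The Study Summary table gives "Number of Subjects 20", a single center and a study duration of 2 years. Its Schema row reads "See attached schema in the appendix section at the end". Section 6.1 makes the same referral: "Please see the appendix for an outline of the study". The text of section 15.0 (Appendices) closes with a label for the patient cohort and N=10 in brackets.

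Section 7.1 is the only place that explains how the sample size was chosen: "Sample size was based upon the average number of cases per year that meet inclusion for the study". It cites past diagnostic and surgical logs as the source and gives no number of any kind.

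Three other statements limit what the 10 could be. Section 5.4 says the study is not randomized and that "All patients will received a helical CT, PET/CT and CBCT". Section 7.3 says "The data from all of the subjects that are enrolled and have consented to be a part of the study will be analyzed". Section 4.5.1 does not foresee early withdrawal.

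Two sections rely on the target without stating it. Section 13.0 starts compilation for publication "Once imaging and histologic data have been collected from the target sample size". Section 10.2.1 places the first independent audit of a study "once they have achieved 10% of target accrual" and a second at 50%.

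**The concern.** The synopsis and the appendix outline are the places where a reader would look for the size of the study, and they show different numbers. The synopsis itself refers to the appendix, so the appendix cannot be set aside as a stray page. Section 7.1 does not resolve the difference, because it names a method of counting and omits the count.

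The target has practical uses. It marks the point at which data collection is complete enough to compile for publication, and it sets the denominator for the audit schedule. If someone working from the appendix outline took 10 as the whole study, compilation would begin at half the number in the synopsis.

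**Working it through.** **Inputs.** Synopsis: 20 subjects, 2 years, one center. Appendix: patient cohort, N=10. Section 7.1: basis is a yearly average, number not given. Section 10.2.1: audits at 10% and 50% of target accrual.

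**Can the plan's own figure be reproduced?** No. Section 7.1 supplies no yearly count or multiplier, and the plan gives no power or precision target from which 20 or 10 could be derived.

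**Direct comparison.** 20 − 10 = 10 patients, so the appendix figure is half the synopsis figure.

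**Does section 7.1 fit one figure better than the other?** Take total = cases per year × years of accrual, where both terms are assumptions:

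- 10 per year × 2 years = 20
- 20 per year × 1 year = 20
- 10 per year × 1 year = 10

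All three agree with the wording of 7.1. The first would link the two printed figures and matches the two-year duration, but a rate of 10 per year is stated nowhere.

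**Could the 10 be part of the 20?** The readable text rules out the usual explanations:

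- Study arm: none exists, since every patient has all three scans (5.4).
- Evaluable subset: none is defined, since all enrolled and consented subjects are analyzed (7.3).
- Attrition: none is foreseen (4.5.1).
- Share per site: the study has one center (Study Summary).

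**Effect on the audit schedule.**

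- N=20: 0.10 × 20 = 2 and 0.50 × 20 = 10, so audits fall at patients 2 and 10.
- N=10: 0.10 × 10 = 1 and 0.50 × 10 = 5, so audits fall at patients 1 and 5.

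**Effect on precision, only if 10 were the total.** The documents give no share of patients with bone invasion, so assume 30%, with a range of 10% to 50%. For a modality that detects every one of n invaded cases, the exact (Clopper-Pearson) 95% lower limit for sensitivity is 0.025^(1/n).

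| Total N | Invaded at 30% | Lower limit | Range, 10% to 50% invaded |
|---|---|---|---|
| 20 | 6 | 0.025^(1/6) = 54.1% | 15.8% (n=2) to 69.2% (n=10) |
| 10 | 3 | 0.025^(1/3) = 29.2% | 2.5% (n=1) to 47.8% (n=5) |

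**The case against.** The strongest reply is that the 10 comes from a diagram that can no longer be read in full. The synopsis promises a schema and section 6.1 promises an outline as well as a card for the offices. The card text is readable. What remains of the outline appears to be the cohort label alone, at the very end of the file, and it may be the first box of a flow chart. A later box could explain it, and content lost in extraction is not a fault of the plan. This stands as a limit on certainty: one can say that the readable text does not reconcile the figures, and no more than that. It does not rescue section 7.1, which is running text with no sign of a gap and has no number whatever the schema shows.

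A second reply is that 20 plainly governs and 10 is the yearly intake. The first half is largely right: no text calls 10 a target, a sample size or a total. The second half is plausible but unstated. If it is true, the defect is a missing label.

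A reader might go further and infer that the study is really planned for 10, or that its precision has been cut by the margin in the table above. The documents do not support either inference. Nothing shows anyone working to 10, and the table rests on an assumed invaded share and a perfect modality. Nor is this an arithmetic error, since the plan contains no sample-size calculation that could be wrong. Whether 20 patients give adequate precision is a separate question; it would remain if both places said 20.

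**Conclusion.** The point holds as an inconsistency in the stated target sample size. Confidence is high that two different figures appear and that 7.1 gives none. It is lower that the complete original leaves them unreconciled, because part of the schema may be missing. On the readable text, 20 is the better-supported target.

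The certain consequence is modest: the publication trigger in 13.0 and the audit points in 10.2.1 rest on a number that the document prints in two versions. Halved enrollment, with the loss of precision that goes with it, would follow only if the appendix figure were used as the total. It should be fixed because a sample size is a figure the study acts on and the correction is cheap.

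**What to change.** State one target N identically in the Study Summary, section 7.1 and section 15.0. That figure should be 20 unless the sponsor confirms otherwise. If the 10 is meant to stay in the appendix, label what it counts, for example eligible cases per year. In 7.1, add the yearly case count taken from the logs and the accrual period, so that their product gives the target.

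If 20 is already the working target, the cost is a few words in an amendment, with no change to enrollment, procedures or analysis. If the sponsor finds that 10 has been used as the total and settles on 20, 10 more patients are needed.

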7.2 Statistical Methods

Sensitivity and specificity of the clinical exam, CBCT, helical CT, PET/CT, MRI and any other imaging modality used in detection of bone invasion will be calculated, as compared to the histological examination of the specimens.

Sensitivity: $[TP / (TP + FN)] \times 100$

Specificity: $[TN / (FP + TN)] \times 100$

Also, the confidence interval will be determined for the sensitivity and specificity.

True positive (TP): pts with histologic and radiographic evidence of invasion

True negative (TN): pts without histologic or radiographic evidence of

invasion

False Positive (FP): pts with positive radiologic evidence of invasion without histologic evidence

False Negative (FN): Those without radiographic evidence of invasion, but with histologic invasion present

In addition, the positive and negative predictive value will be calculated for each modality using the true positive and negatives as well as false positive and negative values.

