1.1 Specific Aims and Hypothesis

There are newer imaging modalities that have not been studied sufficiently to determine whether intraoral SCC has or has not infiltrated a segment of the mandible or maxilla, necessitating partial or complete resection of the jaw. One such modality is cone beam CT (CBCT), which delivers approximately 1/6 the amount of radiation and is about 1/10 the cost of a multi-slice, helical CT¹. A previously published imaging protocol by Van Cann et al² used MRI, CT and bone SPECT to image the mandible. In contrast to the prior algorithm, this study aims to test newer modalities such as the CBCT, PET/CT and helical CT against more traditional imaging techniques, to attempt to detect neoplastic infiltration of the mandible and maxilla. We hypothesize that CBCT or a combination of the aforementioned modalities can be used in order to more accurately predict invasion of the maxilla or mandible by intraoral SCC.

The accurate prediction of the presence or absence of malignant invasion of the jaws greatly influences the surgical treatment plan. This is important for several reasons. First, it may change the staging of the disease, necessitating a more or less involved resection and reconstruction. Second, this knowledge will greatly benefit the surgeon, since the reconstruction of an extensive surgical defect will be more complex and require greater planning. In addition, occult infiltration of the jaws may be a source of locoregional regrowth and recurrence that may be detectable by such imaging, leading to a wider, more appropriate and oncologically sound resection. Third, if absence of mandibular or maxillary invasion can be proven statistically, it will permit “sparing” of complete or partial resection. Thus, the mandible and maxilla, which are critical to facial form and function, will be preserved in some form and improve the overall quality of life of the cancer patient.

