3.3 Secondary Study Endpoints

The secondary endpoint would be to more accurately plan the resection of mandibular or maxillary bone if invasion is predicted. If invasion is not predicted based upon the imaging modalities, then the secondary endpoint would be to spare resection of uninvolved bone

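### Section 7.2 plans confidence intervals for sensitivity and specificity but only point values for PPV and NPV; at N=20 the exact 95% lower limit for NPV cannot exceed 83.2%

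*Combined protocol and SAP*

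**What the plan says.** Section 7.2 (Statistical Methods) defines the four cells of the table against histology and the formulas for sensitivity and specificity. It adds that "the confidence interval will be determined for the sensitivity and specificity", giving neither a confidence level nor a method. The predictive values follow: "In addition, the positive and negative predictive value will be calculated for each modality using the true positive and negatives". No interval is attached to them. The synopsis row on statistical methodology is the same in this respect: "Finally the positive and negative predictive values for each of the imaging modalities will be calculated". No other section supplies an interval for PPV or NPV.

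Two sections give a negative scan its meaning. Section 1.1 says that "if absence of mandibular or maxillary invasion can be proven statistically, it will permit" sparing of complete or partial resection. Section 3.3 says: "If invasion is not predicted based upon the imaging modalities, then the secondary endpoint would be to spare resection of uninvolved bone".

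On size, the synopsis has "Number of Subjects 20", while the appendix outline shows a cohort of N=10. Section 7.1 explains that "Sample size was based upon the average number of cases per year that meet inclusion for the study". It gives no precision target, expected accuracy or expected share of patients with invasion.

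**The concern.** The question behind sections 1.1 and 3.3 is how sure one can be that the bone is free of tumour when the scan is negative. That is the NPV, TN/(TN+FN). Sensitivity and specificity condition on the histology instead, so their intervals do not answer it directly. PPV bears mainly on the decision to resect; it has the same omission but matters less for sparing.

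If the plan is followed literally, a run of correct negative scans would be reported as an NPV of 100% with no interval of its own. With counts this small, such a figure is compatible with a substantial rate of missed invasion, and a reader asking about sparing would look at this number first.

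**Working it through.** **Inputs.** N=20 (synopsis) and N=10 (appendix). The documents give no confidence level, prevalence of invasion or NPV threshold. I assume a two-sided 95% level and, where a split is needed, 30% to 50% of patients with histological invasion. N=20 itself cannot be reproduced, because section 7.1 derives it from caseload and not from a formula.

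**Formula.** For x correct out of n negative scans, the Clopper-Pearson limits are the 2.5% quantile of Beta(x, n−x+1) and the 97.5% quantile of Beta(x+1, n−x). When x = n the upper limit is 1 and the lower limit reduces to 0.025^(1/n).

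**Ceiling.** The lower limit is highest when every patient is test-negative and none has invasion.
- N=20, 20/20: 0.025^(1/20) = 0.832, so 83.2% (Wilson 83.9%; one-sided exact 95% bound 0.05^(1/20) = 86.1%).
- N=10, 10/10: 0.025^(1/10) = 0.692, so 69.2%.

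**Error-free test at N=20, assumed share invaded.**

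| Share invaded (assumed) | Correct negatives | Exact lower limit |
|---|---|---|
| 30% | 14/14 | 0.025^(1/14) = 76.8% |
| 40% | 12/12 | 0.025^(1/12) = 73.5% |
| 50% | 10/10 | 0.025^(1/10) = 69.2% |

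**One missed invasion.** 13/14 = 92.9%, interval 66.1% to 99.8%. 11/12 = 91.7%, interval 61.5% to 99.8%. 9/10 = 90.0%, interval 55.5% to 99.7%.

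**Error-free negatives needed for the two-sided lower limit to reach a threshold t**, n = ceil(ln 0.025 / ln t): 17 for 80%, 23 for 85%, 36 for 90%, 72 for 95%. Only the first fits within 20 patients.

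**Does the planned specificity interval stand in for NPV?** It does only when the denominators agree. Take 20 patients, 6 invaded (30%, assumed), with TP=4, FN=2, TN=14, FP=0. Specificity is 14/14 = 100%, interval 76.8% to 100%. NPV is 14/(14+2) = 14/16 = 87.5%, interval 61.7% to 98.4%. The planned specificity interval would not show the NPV uncertainty here. Sensitivity, 4/6 = 66.7% with interval 22.3% to 95.7%, would warn the reader but is a different quantity.

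**Why the method matters.** The simple normal-approximation interval has half-width 1.96 × sqrt(p(1−p)/n). At p = 1 this is zero for any n, so 14/14 would be shown as 100% to 100%. The exact interval is 76.8% to 100% and the Wilson interval 78.5% to 100%.

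**The case against.** The strongest reply is that this is a one-line omission with little consequence. The plan leaves the intervals out but does not exclude them, and they can be computed at any time from the counts the synopsis already promises. In the error-free case the reader is not left without warning: with 14 uninvolved and 6 invaded patients, specificity is also 14/14 with the same exact interval (76.8% to 100%), and sensitivity is 6/6 with a lower limit of 54.1%. Both intervals are planned. This stands, and it limits the harm. It does not remove the gap, because NPV and specificity part company as soon as their denominators differ.

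A reader might go further and infer that 20 patients cannot meet the standard of proof in section 1.1. The documents do not support that. Section 1.1 is a conditional rationale, not an objective, endpoint or decision rule, and it names no NPV threshold, confidence level or test. A threshold of 80% would be attainable with 17 error-free negatives out of 20, unlikely as that may be.

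A reader might also expect a bare NPV to trigger the release of imaging results to the surgeon under section 8.3. That section speaks only of accurate prediction and does not mention NPV. Its undefined trigger is a separate matter that intervals would not settle. Likewise, the zero-width interval is a risk of leaving the method open, not something the plan has chosen.

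**Conclusion.** The concern holds in a limited form. The plan provides no interval for PPV or NPV, and states neither level nor method for the intervals it does provide. The omission falls on the measure closest to the sparing question.

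The size of the uncertainty is considerable. No NPV above about 83% could be demonstrated at two-sided 95% confidence with 20 patients, or above about 69% with 10. The 83.2% and 69.2% ceilings depend only on N, the 95% level and the exact method. The 76.8% to 69.2% range also rests on an assumed 30% to 50% invasion and a test without error, and the interval after one miss rests on an assumed count of 14 negatives. Results for N=20 and N=10 should not be merged into one range.

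This is something the sponsor should correct. It does not show that the study fails a stated criterion, and it does not by itself require sections 1.1 or 2.1 to be reworded.

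**What to change.** In section 7.2 and the synopsis, specify two-sided 95% Clopper-Pearson (or Wilson) intervals for sensitivity, specificity, PPV and NPV, for each modality, with numerator and denominator shown beside each estimate. Require any conclusion about absence of invasion to quote the lower limit of the NPV interval.

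If section 7.1 is extended to state attainable precision, give the 83.2% ceiling for N=20 and label any figure that depends on prevalence as an assumption. The 20 in the synopsis and the 10 in the appendix should be reconciled first, since the ceiling depends on which applies.

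The cost is a few sentences and a line of analysis code, with no additional patients, scans or data. The downside is that the reported conclusion becomes more modest.

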7.3 Subject Population(s) for Analysis

This section should be very specific in defining the subject populations whose data will be subjected to the study analysis – both for the primary analysis and any applicable secondary analyses.

The data from all of the subjects that are enrolled and have consented to be a part of the study will be analyzed.

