5.6 Subject Compliance Monitoring

In this study, compliance is minimized in that once the imaging is completed and the surgical treatment carried out, the patient will have little commitment to the study.

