15.0 APPENDICES

To be posted in OMFS and JHNS office:

Prediction of Bone Invasion by Squamous Cell Carcinoma:

Inclusion: SCC of the oral cavity

Exclusion:

1. prior mandibular surgery
2. primary intraosseous carcinoma
3. prior history of radiation to the mandible
4. obvious finding of clinical invasion of the mandible,
5. age under 18 years old

Visit I: Screening visit

Visit II: Referral to OMS department for CBCT

Visit III: Definitive Surgical Treatment Plan

Goal:

To determine if any imaging modalities or combination of studies can accurately predict the presence or absence of maxillary or mandibular invasion by oral SCC. The diagnostic imaging will be compared to the histologic investigation of the resected specimens in order to determine their accuracy.

Patient Cohort
(N=10)

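### Sections 7.2 and 7.3 give no rule for a subject whose bone was not examined histologically; depending on the reading, that subject is scored as a true negative or false positive, or drops out unrecorded

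*Combined protocol and SAP*

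**What the plan says.** Section 7.3 keeps the template instruction "This section should be very specific in defining the subject populations" and then answers it in one sentence: "The data from all of the subjects that are enrolled and have consented to be a part of the study will be analyzed". It sets no condition on histology.

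Section 7.2 defines four classes. True positives and false negatives require invasion on histology. A true negative is "pts without histologic or radiographic evidence of" invasion, and a false positive is "pts with positive radiologic evidence of invasion without histologic evidence". There is no fifth class and no substitute reference standard such as follow-up.

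Other text bears on how these definitions should be read. Section 7.2 says accuracy is judged "as compared to the histological examination of the specimens", and the appendix says "The diagnostic imaging will be compared to the histologic investigation of the resected specimens in order to determine their accuracy". Surgery is expected: section 5.6 describes little commitment from the patient "once the imaging is completed and the surgical treatment carried out", and section 7.1 takes the sample size from qualifying cases "based upon previous diagnostic and surgical logs". Section 9.3 asks for missing data to be explained and for procedures not done to be marked N/D. Section 13 expects histologic data from the target sample. None of these requires bone in the specimen or says how to analyse a subject without it.

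**The concern.** Sections 4.1 and 4.2 require oral squamous cell carcinoma and exclude obvious clinical invasion of the mandible. They do not require surgery, bone resection or a tumour near bone. A subject can therefore be enrolled, imaged and even operated on without any bone reaching the pathologist.

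Two different errors can follow. The first is a scoring error: absence of evidence is counted as evidence of absence. The second is partial verification: an invaded jaw that imaging missed and nobody examined never appears as a false negative, whether the subject is scored as a true negative or left out. A scoring rule repairs the first error but not the second.

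The second error depends on what the surgeon knows. Section 1.1 says predicted invasion strongly shapes the surgical plan, section 5.2 says helical CT and PET/CT are in routine use, and section 6.1 blinds planning to CBCT only. Imaging-negatives on the modalities the surgeon sees may therefore be verified less often. Section 1.1 also hopes to support sparing of bone when invasion is absent, a use for which sensitivity and NPV matter most.

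**Working it through.** **Mapping through section 7.2.** Take a subject with no bone histology. Without histologic invasion the subject cannot be a true positive or a false negative. On the literal reading, an imaging-negative result gives a true negative (TN) and an imaging-positive result a false positive (FP). On the specimen reading the subject has no class and leaves the table, although section 7.3 says everyone is analysed.

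**Inputs.** The plan offers no figure to reproduce: section 7.1 rests on case volume and gives no prevalence, accuracy or verification rate. N = 20 is from the Study Summary (the appendix schema shows N=10, a separate matter to reconcile). All other inputs are assumptions: invasion 30%, sensitivity 80%, specificity 85%, with a grid of invasion 20, 30, 40%, sensitivity 70, 80, 90% and specificity 75, 85, 95%.

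**A modality known to the surgeon.** Assume all imaging-positives are verified, and a random share v of imaging-negatives. At v = 0.5, as proportions of all subjects:

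- TP = 0.30 × 0.80 = 0.24; FP = 0.70 × 0.15 = 0.105
- FN = 0.06, of which 0.03 is verified; TN = 0.595, of which 0.2975 is verified
- Sensitivity, either reading: 0.24 / (0.24 + 0.03) = 88.9% (true 80%)
- NPV, literal: (0.595 + 0.03) / 0.655 = 95.4%; verified-only: 0.2975 / 0.3275 = 90.8% (true 90.8%)
- Specificity, literal: 0.625 / 0.730 = 85.6%; verified-only: 0.2975 / 0.4025 = 73.9% (true 85%)

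Errors over the grid, in percentage points:

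| Share of imaging-negatives verified | Sensitivity, either reading | NPV, literal |
|---|---|---|
| 90% | +0.9 to +2.2 | +0.3 to +2.1 |
| 50% | +4.7 to +12.4 | +1.3 to +10.5 |
| 25% | +7.3 to +20.3 | +1.9 to +15.8 |

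At 50%, literal specificity is off by only +0.1 to +2.3 points, while verified-only specificity is off by -4.5 to -15.0.

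**CBCT.** Suppose verification is unrelated to the CBCT result and to true invasion, and half of all subjects are verified. Every verified cell is halved, so verified-only estimates are unbiased (sensitivity 0.12 / 0.15 = 80%). Literal scoring adds the unverified imaging-positives, 0.345 / 2 = 0.1725, to FP and the unverified imaging-negatives, 0.655 / 2 = 0.3275, to TN:

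- Specificity: (0.2975 + 0.3275) / (0.625 + 0.0525 + 0.1725) = 0.625 / 0.850 = 73.5% (true 85%)
- PPV: 0.12 / 0.345 = 34.8% (true 0.24 / 0.345 = 69.6%)
- NPV: 0.625 / 0.655 = 95.4% (true 90.8%)

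**Whole-number illustration, N = 20, for a modality known to the surgeon.** Assume true TP 5, FN 1, TN 12, FP 2, with 6 of the 13 imaging-negatives unverified, including the one false negative.

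| | True | Literal | Verified-only | Bounds |
|---|---|---|---|---|
| Sensitivity | 5/6 = 83.3% | 5/5 = 100% | 5/5 = 100% | 45.5-100% |
| Specificity | 12/14 = 85.7% | 13/15 = 86.7% | 7/9 = 77.8% | 77.8-86.7% |
| NPV | 12/13 = 92.3% | 13/13 = 100% | 7/7 = 100% | 53.8-100% |
| PPV | 5/7 = 71.4% | 5/7 | 5/7 | 71.4% |

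The exact 95% interval is 47.8-100% for 5/5 and 35.9-99.6% for 5/6. Lower bounds set all 6 to invaded (sensitivity 5/11, NPV 7/13, specificity 7/9); upper bounds set none. If the 6 are a random draw from the 13, the false negative is among them with chance 6/13 = 46%. Otherwise literal scoring returns the true values and verified-only specificity is 6/8 = 75.0%.

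**The case against.** The strongest reply is that the literal reading proves too much. By the same logic, a histology-negative subject who never had an MRI would be an MRI true negative, and nobody would score that. Accuracy is to be judged against histology of specimens, so the ordinary meaning of a negative reference is examined and negative, and the N/D convention already separates not done from negative at recording. This stands as far as it goes: a reader might infer that the plan definitely scores unexamined bone as tumour-free, and the documents do not settle that. But the alternative reading states no exclusion, sits badly with section 7.3, and leaves partial verification in place. N/D is a recording rule, not an analysis rule.

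A reader might also infer that sensitivity is inflated for every modality. Section 6.1 does not support this for CBCT, the modality named in the hypothesis. Planning is blinded to it, so any dependence is at most indirect, through agreement with CT, PET/CT or the clinical examination, and its strength is unknown.

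Nor do sections 3.3 and 8.3 show that bone goes unexamined during data collection. The first states an aim of sparing uninvolved bone; the second releases results to the surgeon only once a modality has been found accurate.

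Finally, sampling error at N = 20 dwarfs a bias of a few points, and worst-case bounds can be nearly uninformative, since they count a soft-tissue specimen far from bone as invaded. Both points are fair. They argue for presenting bounds as a sensitivity analysis, not for leaving the rule unstated.

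**Conclusion.** The gap holds: the plan neither requires examined bone for a negative reference nor says what happens to a subject without it. The direction of error depends on the modality.

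- For modalities the surgeon knows (helical CT, PET/CT, clinical examination), if imaging-negatives are verified less often and some are invaded, sensitivity is overstated on either reading. Literal scoring also overstates NPV and barely moves specificity.
- For CBCT, if verification is unrelated to its result and to invasion, dropping unverified subjects does no harm beyond lost precision. Literal scoring lowers specificity and PPV and raises NPV.

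It would go too far to say that these errors will occur or are large. The frequency of unexamined bone cannot be derived from the documents, every magnitude rests on assumed inputs, and the effect is small if nearly all bone is examined. The study is descriptive with no decision threshold, so the harm is misleading accuracy estimates, not a reversed test. Severity: minor to should-fix.

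**What to change.** Amend sections 7.2 and 7.3:

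1. Define true negatives and false positives as subjects whose bone was examined histologically and reported free of tumour. Class subjects without bone histology as not verified. Record bone examined (yes/no) if the CRF, which is not among the documents, does not already do so.
2. Report the number not verified by each modality's result.
3. Report verified-only estimates per modality, labelled as open to verification bias for modalities known to the surgeon. Whenever any subject is not verified, add bounds for sensitivity, specificity, PPV and NPV as a sensitivity analysis. For the lower bounds, set unverified imaging-negatives to invaded and unverified imaging-positives to not invaded; for the upper bounds, do the reverse.

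The cost is some wording, at most one CRF item, and a recount of the same tables. It changes nothing in patient care, and no estimate if all bone is examined. The downside is fewer classified subjects, wide bounds at N = 20, and a verified-only specificity that can lie further from the truth than literal scoring (73.9% against 85.6%, true 85%, in the assumed model). It should therefore always appear with its bounds.
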